## 2. OBJECTIVES AND ENDPOINTS

The trial objectives and endpoints are summarized in [Table 1](#).

**Table 1: Objectives and Endpoints**

Objectives	Endpoints
Primary 
 
To evaluate the efficacy of 2 fixed oral doses (15 mg QD and 30 mg QD) of emraclidine in adult subjects with schizophrenia experiencing an acute exacerbation of psychosis
 
	Primary Endpoint: 
 
Change from Baseline at Week 6 in the Positive and Negative Syndrome Scale (PANSS) total score
 
 Key Endpoint: 
 
Change from Baseline at Week 6 in the Clinical Global Impression-Severity of Symptoms (CGI-S) score
 
 Secondary Endpoints: 
 
Change from Baseline at all time points in PANSS total score
 
Change from Baseline at all time points in CGI-S score
 
Percentage of responders at Week 6 (responders defined as <math>\geq 30\%</math> reduction from Baseline in PANSS total score)
 
 Exploratory Endpoints: 
 
Clinical Global Impression Improvement of Symptoms (CGI-I) at Weeks 3 and 6
 
Change from Baseline at all time points in PANSS positive, negative, and general psychopathology subscale scores
 
Change from Baseline at all time points in PANSS Marder Factor scores
 

Objectives	Endpoints
Secondary	

 
To evaluate the safety and tolerability of 2 fixed oral doses (15 mg QD and 30 mg QD) of emraclidine in adult subjects with schizophrenia experiencing an acute exacerbation of psychosis
 
	
 
Treatment-emergent adverse events (TEAEs)
 
Clinically significant changes in electrocardiograms (ECGs), clinical laboratory assessments and metabolic parameters, standard vital sign measurements, and physical and neurological examination results, including body weight
 
Clinically significant findings in suicidality assessed using the Columbia-Suicide Severity Rating Scale (C-SSRS)
 
Extrapyramidal symptoms evaluated using the change from Baseline in Simpson Angus Scale (SAS), Abnormal Involuntary Movement Scale (AIMS), and Barnes Akathisia Rating Scale (BARS) assessments
 

Exploratory	

 
To evaluate the plasma pharmacokinetics of emraclidine and its metabolite, CV-0000364, following 2 fixed oral doses (15 mg QD and 30 mg QD) of emraclidine in adult subjects with schizophrenia experiencing an acute exacerbation of psychosis
 
To evaluate quality of life and cognition following 2 fixed oral doses (15 mg QD and 30 mg QD) of emraclidine in adult subjects with schizophrenia experiencing an acute exacerbation of psychosis
 
	
 
Pharmacokinetic parameters for emraclidine and its metabolite, CV-0000364 (<math>C_{max}</math> and <math>AUC_{tau}</math>)
 
Change from Baseline at Week 6 in Brief Assessment of Cognition in Schizophrenia (BACS) symbol coding test
 
Change from Baseline at Week 6 in Short Form-6 Dimensions (SF-6D)
 

Abbreviations: AIMS=Abnormal Involuntary Movement Scale; AUC=area under the concentration-time curve; BACS=Brief Assessment of Cognition in Schizophrenia; BARS=Barnes Akathisia Rating Scale; CGI-I=Clinical Global Impression-Improvement of Symptoms; CGI-S=Clinical Global Impression-Severity of Symptoms;  $C_{max}$ =maximum (peak) plasma concentration; C-SSRS=Columbia-Suicide Severity Rating Scale; PANSS=Positive and Negative Syndrome Scale; QD=once daily; SAS=Simpson Angus Scale; SF-6D=Short Form-6 Dimensions.

### 3. KEY ASSESSMENTS AND DERIVATIONS

#### 3.1. Efficacy Assessments

##### 3.1.1. Positive and Negative Syndrome Scale (PANSS)

The PANSS ([Kay et al, 1999](#)) is a clinical scale that has been extensively used as a reliable and valid measure of the negative and positive symptoms of schizophrenia ([Liechti et al, 2017](#)). The scale is used for measuring symptom severity in subjects with schizophrenia and is widely used in clinical trials of antipsychotic medications. The PANSS consists of 3 subscales containing a total of 30 symptom constructs. For each symptom construct, severity is rated on a 7-point scale, with a score of 1 indicating the absence of symptoms and a score of 7 indicating extremely severe symptoms. The symptom constructs for each subscale are as follows:

1. Positive Subscale – delusions, conceptual disorganization, hallucinatory behavior, excitement, grandiosity, suspiciousness/persecution, and hostility
2. Negative Subscale – blunted affect, emotional withdrawal, poor rapport, passive pathetic withdrawal, difficulty in abstract thinking, lack of spontaneity and flow of conversation, stereotyped thinking
3. General Psychopathology Subscale – somatic concern, anxiety, guilt feelings, tension, mannerism and posturing, depression, motor retardation, uncooperative, unusual thought content, disorientation, poor attention, lack of judgment and insight, disturbance of volition, poor impulse control, preoccupation, and active social avoidance

All efforts to ensure the same rater administers the PANSS for a given subject at all time points should be made. The PANSS assessment should be completed prior to all other efficacy scales.

PANSS total score is defined as the sum of scores for each symptom construct per subject per visit.

###### 3.1.1.1. Derivation of PANSS Subscale Score

The subscale score is defined as the sum of scores per subject per visit for all items included in each subscale described above.

###### 3.1.1.2. Derivation of PANSS Marder Scores

Although the PANSS is structured as a scale to assess the 3 dimensions of schizophrenia, retrospective factor analyses have been performed using scores from the 30 individual PANSS items to categorize symptoms into 5 dimensions, which are collectively referred to as Marder Factor scores ([Marder et al, 1997](#)). These 5 dimensions include the following: negative symptoms, positive symptoms, disorganized thought, uncontrolled hostility/excitement, and anxiety/depression.

###### 3.1.1.3. Derivation of PANSS Proportion of Responders

The number and proportion of responders is defined as subjects with 30% reduction from Baseline in the PANSS total score at Week 6 or the early termination visit.

For subjects who discontinue and do not have an early termination visit, the subject's last assessment will be considered.

### **3.1.1.4. Handling of Missing Items from PANSS**

If individual items are missing from a given subscale of PANSS for an individual subject at a given time point, the subscale total will be calculated by prorating the total of non-missing items if the number of missing items is no more than one item of the total number of items in the subscale. The PANSS total for an individual subject at a given time point will be similarly calculated by prorating the total of non-missing items if the number of missing items is no more than three items. If the number of missing items exceeds the specifications above, the subscale score or the total score for the individual subject at that time point will be considered missing.

## **3.1.2. Clinical Global Impression-Severity of Symptoms Scale**

The severity of symptoms for each subject will be rated using the Clinical Global Impression-Severity of Symptoms Scale (CGI-S) (Guy, 1976). To perform this assessment, the investigator (or designee) will answer the following question: "Considering your total clinical experience with this particular population, how ill is the subject at this time?" Response choices are 0=not assessed; 1=normal, not at all ill; 2=borderline ill; 3=mildly ill; 4=moderately ill; 5=markedly ill; 6=severely ill; and 7=among the most extremely ill subjects.

### **3.1.2.1. Derivation of CGI-S Proportion of Responders**

The number and proportion of responders is defined as the following:

- Subjects having  $\geq 1$ -point improvements from Baseline in CGI-S score at the Week 6 visit or the early termination visit. For subjects who discontinue and do not have an early termination visit, the subject's last assessment will be considered.
- Subjects having  $\geq 2$ -point improvements from Baseline in CGI-S score at the Week 6 visit or the early termination visit. For subjects who discontinue and do not have an early termination visit, the subject's last assessment will be considered.

## **3.1.3. Clinical Global Impression-Improvement Scale**

The Clinical Global Impression-Improvement Scale (CGI-I) is an observer-rated scale that will be used to measure the subject's symptom severity compared with before initiation of treatment with IMP (Guy, 1976). It is important to note that the observer or rater will provide their assessment of the subject's current level of symptoms compared with their symptoms at Baseline (Day 1).

The investigator (or designee) will rate the subject's change from Baseline in symptom severity using the following response choices: 0=not assessed, 1=very much improved, 2=much improved, 3=minimally improved, 4=no change, 5=minimally worse, 6=much worse, and 7=very much worse.

### **3.1.4. Brief Assessment of Cognition in Schizophrenia – Symbol Coding Test**

The symbol coding test of the Brief Assessment of Cognition in Schizophrenia (BACS) evaluates the cognitive domain related to processing speed, which is identified as important for clinical trials in schizophrenia. The test consists of subjects matching the numerals 1 to 9 to symbols on an electronic platform over a 90-second period. The outcome measure is the number of correct numerals over the time period and ranges from 0 to 110 ([Keefe et al, 2004](#)).

### **3.1.5. Short Form – 6 Dimensions Version 2.0**

The Short Form-6 Dimensions (SF-6D) is a new, internationally adopted measure for assessing the cost-effectiveness of health care interventions. The SF-6D was developed by reducing the SF-36 to a 6-dimension classification (physical functioning, role participation, social functioning, bodily pain, mental health, and vitality) and developing an algorithm to generate a continuous index for health ([Brazier et al, 2002](#)). The algorithm shows how much value people place on different health limitations, and how they will trade-off between them; for example, how much vitality a subject will sacrifice for a reduction in pain. Version 2.0 of the SF-6D (SF-6Dv2) is an improved version of the SF-6D, the SF-6Dv2 classification system describes more distinct levels of health than SF-6D, changes the descriptions used for a number of dimensions, and provides clearer wording for health state valuation ([Brazier et al, 2020](#)).

## **3.2. Safety Assessments**

### **3.2.1. Adverse Event (AE)**

An AE is defined as any untoward medical occurrence in a subject or clinical trial subject, temporally associated with the use of trial intervention, whether or not considered related to the trial intervention. NOTE: Signs and symptoms and/or abnormal laboratory test result indicating a common underlying pathology/diagnosis should be reported as a single AE.

All adverse events will be recorded on the ADVERSE EVENTS eCRF. Adverse events with missing severity will have the severity imputed as ‘Grade 3’ for the AE tabulations. Adverse events with missing relationship to IMP will have the relationship imputed as ‘Related’ for the AE tabulations if the AE started on or after the first dose of IMP. However, in the data listings these missing severity and/or relationship will be presented as missing.

#### **3.2.1.1. Adverse Event of Special Interest (AESI)**

AESIs are defined as described in Protocol (Version 3.0: 15 March 2023) Section 8.3.7. All AESIs will be recorded as such on the ADVERSE EVENTS page of the eCRF.

#### **3.2.1.2. Treatment-emergent Adverse Event (TEAE)**

Any event reported on the eCRF that occurs on or after the initiation of IMP and up to the completion of follow-up period after discontinuation of IMP is considered treatment emergent. Additionally, it is assumed that an adverse event which was reported to have started on Day 1 without an associated onset time is assumed to be treatment emergent.

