- p. 12-lead ECG assessments will be performed after the participant has been at rest for approximately 3 minutes. At Screening, the average of 3 consecutive ECGs collected 1 to 2 minutes apart will be used to determine participant eligibility; at Baseline, only 1 reading is required for determination of eligibility. At approximately 2 hours following dosing at weekly time points, single 12-lead ECGs will be obtained. Additional ECGs can be performed at the investigator's discretion (eg, if abnormalities are noted).

- q. At Screening and Baseline, blood pressure and heart rate assessments should be performed in order to confirm eligibility (see Exclusion Criterion in [Section 5.2](#)). Triplicate supine heart rate and blood pressure measurements should be taken at approximately 1-minute intervals predose (Day 1 only, Baseline), and at approximately 2 hours after dosing on Day 1 and Weeks 1 through 6. The triplicate supine heart rate and blood pressure measurements will be followed by a single measurement after approximately 2 minutes in a standing position to allow for orthostatic assessments. Additional time points can be added at the investigator's discretion (eg, if abnormalities are noted). Further details are provided in [Section 8.2.3](#) and in the Operations Manual.
- r. The "Baseline/Screening" C-SSRS form will be completed for all participants at Screening to determine eligibility and the "Since Last Visit" C-SSRS form will be completed at Baseline to ensure that the participant continues to qualify for the trial. The "Since Last Visit" C-SSRS form will also be completed at weekly time points after Baseline.
- s. EPS assessments can be completed at any time during the trial, per investigator discretion, if symptoms are present.
- t. Prior and concomitant medications should be recorded from Screening through the participant's last visit/contact.
- u. Adverse events (serious and nonserious) should be recorded from the first dose of IMP through the participant's last visit/contact.
- v. The Week 6 prolactin results will be partially blinded; the investigator will be notified if the prolactin levels exceed a predefined limit with instructions to send the participant for appropriate follow-up.
- w. For women of childbearing potential only. Pregnancy tests can be performed at any time during the trial at the discretion of the investigator if pregnancy is suspected. Any urine pregnancy tests that are positive must be confirmed using a serum test.

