4 TRIAL DESIGN

4.1 Overall Design

This is a Phase 2, multicenter, randomized, double-blind, placebo-controlled, parallel-group, 6-week trial to evaluate the efficacy, safety, and tolerability of 2 fixed doses of emraclidine (15 mg QD and 30 mg QD) in male and female participants aged 18 to 65 years, inclusive, who have schizophrenia and are experiencing an acute exacerbation of psychosis. The trial will include up to a 15-day Screening Period (up to a maximum of 21 days allowed with approval of the medical monitor), a 45-day Inpatient Treatment Period, and a 28-day Follow-up Period. Each participant will participate in the trial for up to approximately 13 weeks.

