4.1.3 Follow-up Period

All participants (completers and early withdrawals), with the exception of those entering the optional open-label rollover trial, will have a follow-up safety contact at approximately 28 days after the last dose of IMP.

Participants may be allowed to stay in the inpatient facility up to 7 days after their last dose of IMP if necessary to achieve stabilization on alternate therapy with review and approval by the medical monitor.

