9.	
Agree to comply with the following contraception requirements during the trial and for 7 days after the last dose of IMP:
 
 • Sexually active men must agree to use a condom and practice contraception during treatment and until the end of relevant systemic exposure (ie, 7 days after the last dose of IMP). • Sexually active women of childbearing potential must use highly effective contraception as defined in Section 10.4.1.1 
In addition, male participants should not donate sperm for a minimum of 7 days following the last dose of IMP.

10.	
Body mass index of 18.0 to 40.0 kg/m² and a total body weight ≥ 50 kg (110 lbs).

11.	
Capable of giving signed informed consent, which includes compliance with the requirements and restrictions listed in the ICF and in Section 10.1.3.

12.	
Ability, in the opinion of the investigator, to understand the nature of the trial, participate in trial visits, and comply with protocol requirements, including the prescribed dosage regimens, scheduled visits, laboratory tests, outcomes measures, and other trial procedures.

Abbreviations: AIMS=Abnormal Involuntary Movement Scale; BARS=Barnes Akathisia Rating Scale; CGI-S=Clinical Global Impression–Severity of Symptoms; DSM-5=Diagnostic and Statistical Manual of Mental Disorders, Fifth Edition; ICF=informed consent form; IMP=investigational medicinal product; MINI=Mini International Neuropsychiatric Interview; PANSS=Positive and Negative Syndrome Scale; SAS=Simpson Angus Scale.

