6.6 Intervention After the End of the Trial

Participants who complete through Day 45 of the trial may have the opportunity to receive open-label treatment with emraclidine in an open-label extension trial

(Protocol CVL-231-2003) if available. Participants who are ineligible or elect not to enter the open-label extension trial will resume treatment with available antipsychotic medications at the discretion of and as determined by their physician.

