### 5.15.1. Adverse Events

Adverse events will be mapped to MedDRA version 26.0 or higher preferred term and system organ class. If a subject experiences multiple events that map to a single preferred term, the greatest severity and strongest investigator assessment of relation to IMP will be assigned to the preferred term for the appropriate summaries. Events with missing severity or relationship will be classified as outlined in [Section 3.2.1](#). Summaries of treatment-emergent AEs will include any AEs reported beginning with the initiation of study drug on Day 1 through the follow up contact. An overall summary of TEAEs, including the number of subjects with a TEAE, TEAE related to IMP, AESI, serious TEAE, serious TEAE related to IMP, TEAE leading to discontinuation of

IMP, and TEAE leading to death will be summarized. [REDACTED]

[REDACTED] The occurrence of treatment emergent adverse events (TEAEs) will be summarized by treatment group using preferred terms, system organ classes, and severity. Separate summaries of TEAEs, treatment-emergent serious adverse events (TESAEs), TEAEs related to IMP, AESIs, events leading to discontinuation of IMP will be generated by system organ class and preferred term.

Treatment-emergent adverse events with  $\geq 2\%$  incidence in either one of the emraclidine arms and a greater incidence than the placebo arm will be summarized by preferred term. The most common TEAEs in either one of the emraclidine arms, defined as an incidence  $\geq 5\%$  and greater than 2 times of the incidence in the placebo group, will also be summarized by treatment group using preferred term. [REDACTED] All

adverse events reported will be listed for individual subjects showing both verbatim and preferred terms. All adverse events that occurred prior to the initiation of study treatment will be excluded from the tables but will be included in the listings.

Missing onset dates will be imputed as previously outlined in [Section 4.1.12](#) as required to determine treatment-emergent events.

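### TEAE tables run through a 28-day post-dose follow-up that rollover participants do not have: add on-treatment TEAE tables and an end date for rollover participants

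*SAP*

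**What the plan says.** SAP 3.2.1.2 sets the window: any reported event on or after first dose and "up to the completion of follow-up period after discontinuation of IMP is considered treatment emergent". SAP 5.15.1 carries it into the summaries, which take in "any AEs reported beginning with the initiation of study drug on Day 1 through the follow up contact". That section also defines the displays that set the arms against each other. One is a list of common TEAEs, which requires at least 5% incidence in an emraclidine arm and an incidence "greater than 2 times of the incidence in the placebo group".

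Protocol 4.1 plans "a 45-day Inpatient Treatment Period, and a 28-day Follow-up Period". The Schedule of Assessments places the follow-up contact at Day 73 (±3), by telephone or similar means. Under Protocol 4.1.3 all participants, "with the exception of those entering the optional open-label rollover trial, will have a follow-up safety contact at approximately 28 days" after the last dose. Collection follows the same calendar: "Adverse events (serious and nonserious) should be recorded from the first dose of IMP through the participant's last visit/contact" (Schedule of Assessments footnote). For a rollover participant, the last contact in this trial is at about Day 45.

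After Day 45, completers who are ineligible or "elect not to enter the open-label extension trial will resume treatment with available antipsychotic medications" (Protocol 6.6). For men, the contraception requirement in Protocol 5.1 (criterion 9) runs "until the end of relevant systemic exposure (ie, 7 days after the last dose of IMP". SAP 3.2.7 treats a drug started after the last IMP dose as not concomitant.

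The visible SAP text gives no TEAE end date for rollover participants, no separation of onsets before and after last dose, and no exposure-adjusted rate. SAP 5.15.1 has redacted sentences, and SAP Table 3 has a redacted population used for some safety outputs, so a further summary may exist.

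**The concern.** TEAEs are the first-listed endpoint under the safety objective. Three features of the window affect how the arms compare.

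- **Its length depends on a choice made after randomisation.** Only completers can roll over, entry is optional, and the extension must be available. The choice may be related to response or tolerability, and so to arm.
- **The longer window contains time off the study drug.** For many participants this will be time on another antipsychotic. An adverse event of that drug counts as treatment emergent for the randomised arm, although SAP 3.2.7 does not count the drug itself as concomitant.
- **The definition is incomplete.** For rollover participants the follow-up contact that closes the window does not take place in this trial, so an end date has to be chosen at programming.

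At stake is how the active-versus-placebo safety tables are read. The PANSS and CGI-S tests and the sample size are unaffected.

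**Working it through.** **Inputs from the documents.** Treatment lasts 45 days and follow-up 28 days (Protocol 4.1). The sample size section gives 93 completers per arm and 25% discontinuation (Protocol 9.5). The exposure limit is 7 days after last dose (Protocol 5.1), and the half-life is 9.4 to 12.2 hours (Protocol 2.2.3).

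**Assumptions, because the documents give no figure.** These are the rollover share among completers, the mean discontinuation day (Day 21 unless varied), and the event risks.

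**1. The plan's own figures.** 45 + 28 = 73, which matches the scheduled Day 73. 93 / 0.75 = 124 per arm, so 31 per arm discontinue, and 3 × 124 = 372. Both reproduce.

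**2. Window per participant.** A completer who rolls over has about 45 days and one who does not has about 73, a ratio of 73/45 = 1.62. In the longer window 28/73 = 38% is after the last dose. Beyond the protocol's exposure limit lie 28 − 7 = 21 days. Five half-lives are 5 × 9.4/24 = 2.0 to 5 × 12.2/24 = 2.5 days. An early terminator at Day 21 has 21 + 28 = 49 days.

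**3. Observation time by arm.** On-drug time is 93 × 45 + 31 × 21 = 4,836 person-days in each arm. Follow-up adds 28 × [31 + 93 × (1 − rollover share)].

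| Rollover, active vs placebo | Follow-up days | Total days | Placebo excess, total |
|---|---|---|---|
| 50% vs 50% | 2,170 vs 2,170 | 7,006 vs 7,006 | 0% |
| 70% vs 50% | 1,649 vs 2,170 | 6,485 vs 7,006 | 8.0% |
| 70% vs 30% | 1,649 vs 2,691 | 6,485 vs 7,527 | 16% |

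For 70% vs 50%, moving the mean discontinuation day from 7 to 38 changes on-drug time to 4,402 or 5,363 days, and the excess to 521/6,051 = 8.6% or 521/7,012 = 7.4%.

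**4. Between-arm distortion with no drug effect.** Assume a constant hazard, a 20% event risk over 45 days, and the same hazard in follow-up. Risk is 1 − 0.8^(45/45) = 20.0% for a rollover completer, 1 − 0.8^(73/45) = 30.4% for another completer, and 1 − 0.8^(49/45) = 21.6% for an early terminator. Arm risk = 0.75 × [r × 20.0% + (1 − r) × 30.4%] + 0.25 × 21.6%, where r is the rollover share.

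- Equal rollover: 0 points.
- 70% vs 50%: 22.7% vs 24.3%, −1.6 points.
- 70% vs 30%: 22.7% vs 25.8%, −3.1 points (ratio 0.88). With 45-day risks of 5% to 40% and a follow-up hazard of 0.5 to 2 times the on-drug hazard, the range is −0.5 to −8.5 points.

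**5. Dilution with equal rollover and a real drug effect.** Take on-drug risks of 10% vs 4% (ratio 2.5) and a follow-up risk q common to both arms. The share with follow-up is f = 0.75 × (1 − r) + 0.25. The full-window risks are 0.10 + 0.90qf and 0.04 + 0.96qf. At q = 3% the ratio is 2.10, 2.02 and 1.94 for rollover of 70%, 50% and 30%. In the last case the term leaves the common-TEAE list. For rollover between 30% and 70%, q = 1% gives 2.26 to 2.34 and q = 5% gives 1.75 to 1.93. The risk difference hardly moves: at q = 3% and 30% rollover it is 12.1% − 6.2% = 5.9 points, against 6.0 on drug.

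**The case against.** The strongest reply is that this is a legitimate choice of window. It matches the protocol's collection period, it catches delayed harms, and the tables test nothing. That stands, and it is why the full-window tables should stay.

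Other points carry weight:

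- **Size.** A reader might compare follow-up time alone and conclude that placebo is observed 32% longer (2,170/1,649). Incidence is counted over the whole window, where the same assumptions give 8%.
- **Follow-up days are not equivalent to inpatient days.** Follow-up is a single remote contact, and scheduled weight, EPS, ECG, vital-sign and laboratory assessments end at Week 6 or early termination. Weight and EPS have their own model-based analyses (SAP 5.15.4.2 and 5.15.8), which the TEAE window does not touch.
- **Existing safeguards.** There are summaries of TEAEs related to IMP, listings of all events, and a summary of medications taken after last dose (SAP 5.15.1 and 5.15.2). These help in part. Relatedness is the investigator's judgement, and a missing value is imputed as related (SAP 3.2.1).
- **Fragile list.** A reader might infer that the window makes the common-TEAE list unreliable, because one more placebo case turns 7/124 vs 3/124 (ratio 2.33) into 7/124 vs 4/124 (1.75). Any ratio rule does this near its boundary, whatever the window.
- **Other antipsychotics.** A reader might take all 21 days beyond the exposure limit as time on another antipsychotic. Protocol 6.6 leaves resumption to the physician, gives no start date, and covers completers only.
- **On-treatment time is unequal too.** If 20% discontinued in one arm and 35% in the other, at Day 21 on average, mean on-drug windows would be 0.80 × 45 + 0.20 × 21 = 40.2 and 0.65 × 45 + 0.35 × 21 = 36.6 days, about 10% apart. So an on-treatment table should be added rather than substituted, with exposure shown beside it.

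**Conclusion.** The point holds as a gap in definition and presentation. Once the extension is open, completers contribute about 45 or about 73 days, the extra 28 days are off drug, and the visible SAP neither separates them nor says where the window ends for rollover participants. The likely effect is some dilution of active-to-placebo ratios. Its size depends on the follow-up event risk, which the documents do not give.

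A reader might go further and infer that the TEAE comparison is biased in favour of emraclidine. The documents do not support that. They give no rollover rate, overall or by arm, and no direction. With equal rollover, equal discontinuation and no drug effect the distortion is zero. If active participants rolled over less than placebo participants, the bias would run the other way. The 8% difference in observation rests on assumed rollover of 70% vs 50% and mean discontinuation at Day 21.

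The displays are descriptive, and the redacted text may already hold an on-treatment summary. This is an inexpensive improvement to the safety tables and does not threaten the trial's conclusions on efficacy.

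**What to change.** In SAP 3.2.1.2 and 5.15.1:

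1. Keep the present full-window TEAE tables, and state the TEAE end date for participants who enter the extension.
2. Add between-arm tables limited to onset from first dose through last dose: overall summary, system organ class and preferred term, the 2% list, and the list requiring at least 5% and more than twice placebo.
3. Tabulate events with onset after last dose separately, at 0–7 days and more than 7 days, by rollover status.
4. Show exposure time by arm beside the on-treatment tables, because their window is still shorter for early terminators.

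The cost is SAP wording and one extra set of tables from data already collected. The downside is that late-onset or withdrawal events do not appear in the on-treatment tables and have to be read from the separate one. Settling this before unblinding avoids a choice of window made after the results are known. If a redacted passage already provides such a summary, only the end date and any missing displays need adding.
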